1.1. Synopsis

ISA Title:

Randomized, Placebo-Controlled, Phase 2 Clinical Trial to Evaluate LY3857210 for the Treatment of Diabetic Peripheral Neuropathic Pain

Brief Title: Phase 2 Clinical Trial to Evaluate LY3857210 for the Treatment of Diabetic Peripheral Neuropathic Pain

Regulatory Agency Identifier Numbers:

LY3857210 IND: 156411

Master Protocol IND: 144915

Rationale:

The purpose of this study is to test whether LY3857210 is efficacious in decreasing diabetic peripheral neuropathic pain (DPNP). LY3857210 is a small molecule receptor antagonist of the P2X7 receptor, an adenosine triphosphate ligand-gated ion channel known to be involved in neuroinflammation and pain.

Data will be collected to assess the safety and tolerability of LY3857210 in this study population. The pharmacokinetics of LY3857210 will also be explored. The totality of data from this proof-of-concept study will assess the benefits and risks associated with LY3857210 and inform decisions for the clinical development of LY3857210.

Objectives, Endpoints, and Estimands:

The primary and secondary objectives and endpoints are stated in the Master Protocol H0P-MC-CPMP (CPMP) and the DPNP disease-state addendum (DSA; H0P-MC-CPMP[3]).

Overall Design:

This is a 10-week Phase 2, randomized, double-blind, placebo-controlled study that will compare LY3857210 versus placebo in participants with DPNP.

Study Population:

In addition to inclusion and exclusion criteria described in Master Protocol CPMP and DSA CPMP(3), individuals may not take part in the study if they have

• an eGFR of less than 30 mL/min/1.73 m.

Number of Participants:

Up to approximately 125 participants will be randomly assigned to study intervention with the assumption that 20% of the participants will drop out prior to the end of the double-blind treatment period.

Intervention Groups and Duration:

This double-blind study includes an 8-week treatment period with a 2-week follow-up visit off treatment.

Intervention Name	LY3857210	Placebo
Dosage Level(s)	45 mg daily	Not applicable
Route of Administration	PO	PO
and Duration		

Abbreviation: PO = by mouth.

[figure not shown]
Ethical Considerations of Benefit/Risk:

Taking into account the measures taken to minimize risk to participants participating in this study, the potential risks identified in association with LY3857210 are justified by the anticipated benefits that may be afforded to participants with DPNP.

Data Monitoring Committee: Yes

Safety reviews are covered by the Assessment Committee charter for the Chronic Pain Master Protocol (CPMP).

1.2. Schema

Abbreviations: PDEP = preliminary data entry period; V = visit.

- ^a Medication washout and PDEP begins.
- ^b Randomization to either LY3857210 or placebo.

1.3. Schedule of Activities (SoA)

This SoA shows visits and procedures unique to the intervention-specific appendix (ISA) H0P-MC-NP05 for LY3857210. Please refer to Master Protocol CPMP and the DPNP DSA CPMP(3) SoAs for additional information.

	Scre	ening	Randomiza tion to ISA			Double-Blind Treatment			F/U	Notes
	V1	V2	V3	V4	V5	V6	V7	ED	V801	
Study Week	Up to -6 months	-10 to -7 days for most participants	0	2	4	6	8		+2	
Visit Window (days)					±	:3			±3	
Confirm ISA inclusion and exclusion criteria	X	X	X							
Physical examination			X		X		X	X	X	Physical examination (see Section 8.2.1). Complete physical examination, including targeted examination specified below, should be performed at V3 and V801 or ED. Targeted physical examination for skin, gastrointestinal tract, mammary gland in males, and lymph nodes should also be performed at V5 and V7.
Neurological assessment			X	X	X	X	X	X	X	See Section 8.2.1.
Prespecified DPNP medical history			X							Includes diagnosis and symptom onset date.
Vital signs			X	X	X	X	X	X	X	At V3, vitals should be taken predose. Pulse rate, respiratory rate, blood pressure, and temperature taken with participant in a sitting position.
Concomitant medication									X	See footnote a.
AE									X	See footnote a.
ECG (single)					X		X	X	X	

form.

X

X

See footnote a.

See footnote a.

Review eDiary compliance.

Review assessment of pain. See MoO for additional details.

NRS for pain

Reinforce pain

reporting

assessment guidelines

Rescue medication usage

	Scre	ening	Randomiza tion to ISA			e-Blind tment	l		F/U	Notes
	V1	V2	V3	V4	V5	V6	V7	ED	V801	
Study Week	Up to -6 months	-10 to -7 days for most participants	0	2	4	6	8		+2	
Visit Window (days)					+	3			±3	
Placebo response video training (participant)		X								Should view at the beginning of V2.
Study intervention administration			X	X	X	X				See Section 6.1. Participant should be instructed NOT to take study intervention on the day of V7.
Dispense study intervention to participant			X	X	X	X				
Participant returns unused study intervention				X	X	X	X	X		Participant to bring study intervention to every visit.
Intervention compliance				X	X	X	X	X		
Scales, Questionnaires, an	nd Outcome M	easures	l	l	 	 	_	_		I
CCI										
C-SSRS Since Last Visit									X	See footnote a.
Self-Harm Supplement form									X	See footnote a.
Self-Harm Follow-Up form									X	See footnote a. Complete 1 form for each event identified on the Self-Harm Supplement

X

X

X

X

[figure not shown]
X

X

	Scre	ening	Randomiza tion to ISA	Double Billia							F/U	Notes
	V1	V2	V3	V4	V5	V6	V7	ED	V801			
Study Week	Up to -6 months	-10 to -7 days for most participants	0	2	4	6	8		+2			
Visit Window (days)					±	:3			±3			
PGI									X	See footnote a.		
Clinical Laboratory Tests	s and Sample C	Collection										
Hematology				X	X	X	X		X			
Chemistry				X	X	X	X		X			
Lipid panel				X	X	X	X		X			
Urinalysis							X		X			
Urine pregnancy			X	X	X	X	X	X		For all WOCBP at V3: collect sample within 24 hours prior to dosing.		
Urine drug screen			X		X		X	X		See Section 5.3.1.		
HbA1c			X				X	X				
HbA1c			X				X	X		A4 V/2 - DIV1 -1111 - 4-1		
LY3857210 PK sample			X	X	X	X	X	X		At V3, a PK sample should be taken any time after 1 hour postdose and prior to leaving the site. At V4, V5, V6, V7 and ED, a PK sample can be taken at any time during the site visit. The date and time of each PK sample collected will be recorded. The date and time of LY3857210 administration prior to the PK sample collection will be recorded.		
CCI												

	Screening Randomiza tion to ISA		Randomiza tion to ISA		Double Treat	e-Blind ment			F/U	Notes
	V1	V2	V3	V4	V5	V6	V7	ED	V801	
Study Week	Up to -6 months	-10 to -7 days for most participants	0	2	4	6	8		+2	
Visit Window (days)					±3			±3		

Participant Devices

Abbreviations: AE = adverse event; CCI ; DPMP = diabetic peripheral neuropathic pain; ECG = electrocardiogram; ED = early discontinuation; F/U = follow-up; HbA1c = hemoglobin A1c; ISA = intervention-specific appendix; MoO = Manual of Operations; NRS = numeric rating scale; PGI = patient's global impression of change; PK = pharmacokinetic; V = visit; WOCBP = women of childbearing potential.

a Collect in addition to schedule described in Master Protocol CPMP.

2. Introduction

This ISA, H0P-MC-NP05 (NP05) is an appendix to Master Protocol H0P-MC-CPMP (CPMP) and contains unique study elements specific for LY3857210. The master protocol contains the overarching study elements that govern the DPNP DSA CPMP(3) and this ISA NP05.

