4.1. Overall Design

Master Protocol CPMP describes the overall study design and study design rationale. This section describes visits and overall procedures unique to ISA NP05 for LY3857210 in addition to the procedures outlined in CPMP and CPMP(3).

Double-blind treatment period (Visits 3 through 7)

Each visit is an outpatient visit.

At Visit 3,

- participants are randomly assigned to LY3857210 or placebo
- the site completes the NP05 baseline procedures and sample collection (excluding PK) prior to study intervention
- the site collects participants' vitals predose
- participants receive their oral study intervention
- the site completes PK sample collection, and
- the site instructs participants to continue with study restrictions and NRS diary entries before their visit discharge.

At Visits 4 through 7,

- the site reviews available safety data and sample collection
- participants continue oral study intervention (not applicable for Visit 7) and bring all study intervention bottles to each visit
- the site completes all sample collection and safety monitoring noted in the SoAs, and
- the site instructs participants to continue with study restrictions, NRS diary entries, and wearing of CCI before their visit discharge.

Double-blind post-treatment follow-up period (Visit 801)

- Participants must complete 1 post-treatment follow-up visit for safety and efficacy assessment at Visit 801 according to the SoA
- the site schedules Visit 801 approximately 2 weeks after Visit 7 or ED Visit, and
- at Visit 801, participants return the devices CCI

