10.4.2. Contraception Guidance

WOCBP who are completely abstinent as their preferred and usual lifestyle, or in a same-sex relationship as their preferred and usual lifestyle:

Must	Must not
agree to either remain abstinent or stay in a same-sex relationship without sexual relationships with males	 use periodic abstinence methods calendar ovulation symptothermal, or post-ovulation declare abstinence just for the duration of a trial, or use the withdrawal method

WOCBP who are NOT completely abstinent as their preferred and usual lifestyle, or NOT in a same-sex relationship as their preferred and usual lifestyle, must do the following:

Topic	Condition
Pregnancy testing	Have a negative serum test result at screening followed by a negative urine result within 24 hours prior to treatment exposure. See the Master Protocol CPMP and the NP05 Schedule of Activities for subsequent pregnancy testing requirements.
Contraception	Agree to use 1 highly effective method of contraception, or a combination of 2 effective methods of contraception.
	These forms of contraception must be used for the duration of the study.

Examples of different forms of contraception:

Methods	Examples
Highly effective contraception (less than 1% failure rate)	 female sterilization combination oral contraceptive pill progestin-only contraceptive pill (mini-pill) implanted contraceptives injectable contraceptives contraceptive patch (only women <198 pounds or 90 kg) total abstinence vasectomy (if only sexual partner) fallopian tube implants (if confirmed by hysterosalpingogram) combined contraceptive vaginal ring, or intrauterine devices
Effective contraception	 male or female condoms with spermicide diaphragms with spermicide or cervical sponges barrier method with use of a spermicide condom with spermicide diaphragm with spermicide, or female condom with spermicide
Ineffective forms of contraception whether used alone or in any combination	 spermicide alone periodic abstinence fertility awareness (calendar method, temperature method, cervical mucus, or symptothermal) withdrawal postcoital douche, or lactational amenorrhea

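### The NP05 schedule has no urine pregnancy test at Visit 801, so a conception late in dosing could go untested; the gap is probable, low priority and cheap to close

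*Protocol*

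**What the plan says.** The urine pregnancy row of the Schedule of Activities (SoA, Protocol Section 1.3) is marked at V3, V4, V5, V6, V7 and ED. Its V801 cell is empty. The row's only note is "For all WOCBP at V3: collect sample within 24 hours prior to dosing". In the same block of the table, hematology, chemistry, lipid panel and urinalysis are all marked at V801.

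The study intervention row states: "Participant should be instructed NOT to take study intervention on the day of V7". The last dose is therefore due the day before V7.

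Section 4.1 makes V801 compulsory: "Participants must complete 1 post-treatment follow-up visit for safety and efficacy assessment at Visit 801 according to the SoA". On timing it says "the site schedules Visit 801 approximately 2 weeks after Visit 7 or ED Visit", and the SoA gives a window of 3 days either side.

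Section 10.4.2 says of contraception: "These forms of contraception must be used for the duration of the study". Section 8.3.1 requires pregnancies arising during participation to be recorded and followed to outcome, whether or not the participant stays on drug or in the study.

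Two statements limit what the blank cell can show. The SoA opens with "This SoA shows visits and procedures unique to the intervention-specific appendix (ISA) H0P-MC-NP05 for LY3857210". Section 10.4.2 adds: "See the Master Protocol CPMP and the NP05 Schedule of Activities for subsequent pregnancy testing requirements". The Master Protocol is not among the documents.

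**The concern.** During dosing, tests come about every two weeks. A conception too recent to show at V4, V5 or V6 is therefore picked up at the next visit, about 14 days later. Only the stretch before V7, or before ED, has no such second look in the NP05 schedule, although a compulsory visit falls about two weeks afterwards and urine is already taken there.

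What is at stake is ascertainment. A pregnancy exposed to study drug near the end of dosing would enter the Section 8.3.1 follow-up only if the participant noticed it and told the site. By V801 the exposure has already happened, so a test there would not prevent it. It would make it more likely that the pregnancy is recorded and its outcome learned.

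**Working it through.** The documents state no figure on this point, so there is none to reproduce. The check is a day count.

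**Inputs**
- First dose on day 0 (V3) and V7 on day 56 (8 weeks, SoA).
- Last dose on day 55 (no dose on the V7 day), giving 56 dosing days.
- V801 nominally on day 70, window days 67 to 73 when V7 is on day 56 (SoA, Section 4.1).
- Detection lag L, the days from conception until a urine test is positive. It is **assumed** to be 10 to 14, with 7 to 21 as a wider range.

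**Rule.** A test on day T detects conceptions up to day T − L. Dosing days not covered = max(0, 55 − (T − L)).

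**Schedule as marked (last test at V7, T = 56).** The formula reduces to L − 1.

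| L (assumed) | Dosing days not covered | Share of 56 |
|---|---|---|
| 7 | 6 | 10.7% |
| 10 | 9 | 16.1% |
| 14 | 13 | 23.2% |
| 21 | 20 | 35.7% |

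The 3-day window around V7 moves the last dose with the visit, so the counts do not change.

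**After ED.** If ED falls d days after the last dose, max(0, L − d) dosing days are not covered. For L of 10 to 14 this is 9 to 13 days at d = 1 and 3 to 7 days at d = 7.

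**With a test at V801.**
- T = 70: 0 days not covered for L = 7, 10 or 14, since 55 − (70 − 14) is below zero. For L = 21, 6 days remain.
- T = 67 (early edge of the window): 55 − (67 − 14) = 2 days remain for L = 14, and none for L = 7 or 10.
- V801 14 days after ED: max(0, L − d − 14) = 0 for L = 10 or 14 at any d of 0 or more.

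**Does the Master Protocol cover V801?** It can only be inferred. Footnote a reads "Collect in addition to schedule described in Master Protocol CPMP". It is attached to adverse events, concomitant medication, the suicidality scale and the global impression of change, which are marked in this SoA only at V801. If the Master Protocol schedule reached V801, adverse event collection would hardly need to be added there. The pregnancy row also carries its own marks at every visit from V3 to ED and stops only at V801, so it does not look like a row left to the Master Protocol. However, footnote a is not attached to that row, so this is not proof.

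**The case against.** The strongest objection is that a blank cell in this SoA does not show that a test is absent. Section 10.4.2 requires a negative serum test at screening, yet the NP05 SoA has no serum pregnancy row. Exclusion [3077] needs an eGFR at Visit 1 or 2, yet chemistry is blank at both. Adverse events are unmarked from V3 to V7. The Master Protocol evidently supplies some of what this table leaves out. That stands as a reason for caution. But these examples all concern visits that the Master Protocol schedule appears to cover, whereas footnote a suggests that V801 lies beyond it.

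A second objection also largely stands. The 9 to 13 days are the assumed lag minus one, and nothing in the documents fixes that lag. A reader might take the 16% to 23% as the chance of missing a pregnancy. It is not: it is a share of dosing days. The number of WOCBP is not given, so no expected count can be stated.

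Third, safeguards exist. WOCBP who are not abstinent must use effective contraception throughout the study, tests are frequent during dosing, and V801 includes adverse event review and a complete physical examination, so there is an occasion for self-report. The documents supplied contain no reproductive-toxicity finding or half-life that would make stopping at V7 or ED unsafe. This lowers the priority but does not replace a test.

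Finally, a V801 test would not cover the whole follow-up period. On day 70 it would still miss conceptions on 9 (L = 10) to 13 (L = 14) of the 14 off-drug days 56 to 69. Its value is for conceptions during dosing.

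**Conclusion.** The point holds as a probable gap of low priority. As marked, the NP05 schedule ends pregnancy testing one day after the last dose in participants who complete treatment, or at ED. With an assumed lag of 10 to 14 days, conceptions on about the last 9 to 13 dosing days could escape every NP05-scheduled test; over lags of 7 to 21 days the range is 6 to 20.

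A reader might go further and conclude that the trial has no pregnancy test at all after dosing, or that participants are left at material risk. The documents support neither. The first depends on the Master Protocol, which was not supplied. The second would need the number of WOCBP, a pregnancy rate and toxicity information, none of which is given. The event is expected to be rare under the contraception requirement, and no endpoint, power calculation or error rate is affected.

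**What to change.** In the NP05 SoA, mark V801 for WOCBP in the urine pregnancy row and test the urine already collected there for urinalysis. Because V801 also follows ED, the same mark covers participants who stop early.

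Make the edit directly. If the Master Protocol already requires a test at V801, the mark is redundant but harmless.

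The cost is one test strip per WOCBP at an existing visit (at most about 125 strips, since that is the total planned enrolment, and fewer in practice) plus one SoA cell. The summary of changes shows that SoA edits are made by amendment, so this one should wait for the next amendment; it does not justify one of its own.

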2.1. Study Rationale

The purpose of this study is to test whether LY3857210 is efficacious in decreasing DPNP. Data will be collected to assess the safety and tolerability of LY3857210 in this study population. The PK of LY3857210 will also be explored. The totality of data from this POC study will assess the benefits and risks associated with LY3857210 and inform decisions for the clinical development of LY3857210.

2.2. Background

P2X7 is an adenosine triphosphate (ATP) ligand-gated ion channel that when activated results in Ca²⁺ influx, and cellular activation (for example, caspase 1). For a recent review article, see Zhang et al. 2020. Stimulation of P2X7 plays a key role in the cross talk of the glial cells and neurons at an over-active synapse and in neuroinflammatory conditions (Currò et al. 2020). Thus, inhibition of the P2X7 receptor found on glial cells in the brain and spinal cord is anticipated to decrease synaptic transmission.

LY3857210 is an orally administered small-molecule receptor antagonist of the P2X7 receptor.

2.3. Benefit/Risk Assessment

More detailed information about the known and expected benefits and risks and reasonably expected AEs of LY3857210 may be found in the IB.

2.3.1. Risk Assessment

Study intervention

Toxicology studies and NOAEL exposure

Based on the observed convulsion in the 3-month dog toxicology study (reported in 1 dog) as well as convulsion noted in the rat in vivo micronucleus study (reported in 1 rat), a 10-fold

exposure multiple based on the observed AUC and C_{max} associated with the NOEL for convulsions in dog (the most sensitive species) will be maintained in this study

In addition, neurological examination will be conducted at regular intervals during the study period and AEs related to CNS signs and symptoms will be collected during the study. Participants with a history of seizures will be excluded from the study.

Potential drug-drug interactions

Clinical drug-drug interaction studies have not been conducted with LY3857210. Based on current in vitro data, LY3857210 is a potential inducer of CYP3A4, CYP1A2, CYP2B6, and CYP2C8. To mitigate risk, participants taking sensitive substrates with a narrow therapeutic index are excluded. See Section 5.2 for exclusion criteria and refer to IB for more information.

Information on AEs expected to be related to the study intervention may be found in the IB . Information on SAEs that are expected in the study population independent of drug exposure will be assessed by the sponsor in aggregate, periodically during the course of the study, and may be found in the IB.

2.3.2. Benefit Assessment

Potential benefits for the study participants include:

- information obtained from study-related medical procedures
 - o physical examinations
 - o laboratory tests, and
 - o ECGs.
- detailed evaluations of diabetic nerve pain, and
- questionnaires that may improve participants understanding their own condition.

As part of Study CPMP, participants in this ISA will report their experience using standard tools that may contribute to the assessment of novel treatments for DPNP. In addition, data collected from this study may also improve our understanding of DPNP pathogenesis. Both of which may lead to the development of new treatment with improved safety and efficacy profile compared to standard of care.

2.3.3. Overall Benefit Risk Conclusion

Taking into account the measures taken to minimize risk to participants participating in this study, the potential risks identified in association with LY3857210 are justified by the anticipated benefits that may be afforded to participants with DPNP.

3. Objectives, Endpoints, and Estimands

The CPMP Master Protocol and DPNP DSA CPMP(3) include objectives and endpoints applicable for this study. This table describes objectives and endpoints specific for LY3857210.

4. Study Design

4.1. Overall Design

Master Protocol CPMP describes the overall study design and study design rationale. This section describes visits and overall procedures unique to ISA NP05 for LY3857210 in addition to the procedures outlined in CPMP and CPMP(3).

Double-blind treatment period (Visits 3 through 7)

Each visit is an outpatient visit.

At Visit 3,

- participants are randomly assigned to LY3857210 or placebo
- the site completes the NP05 baseline procedures and sample collection (excluding PK) prior to study intervention
- the site collects participants' vitals predose
- participants receive their oral study intervention
- the site completes PK sample collection, and
- the site instructs participants to continue with study restrictions and NRS diary entries before their visit discharge.

At Visits 4 through 7,

- the site reviews available safety data and sample collection
- participants continue oral study intervention (not applicable for Visit 7) and bring all study intervention bottles to each visit
- the site completes all sample collection and safety monitoring noted in the SoAs, and
- the site instructs participants to continue with study restrictions, NRS diary entries, and wearing of CCI before their visit discharge.

Double-blind post-treatment follow-up period (Visit 801)

- Participants must complete 1 post-treatment follow-up visit for safety and efficacy assessment at Visit 801 according to the SoA
- the site schedules Visit 801 approximately 2 weeks after Visit 7 or ED Visit, and
- at Visit 801, participants return the devices CCI

